Pentoxifylline Treatment in
Acute Pancreatitis: A Double-
Blind Placebo-Controlled
Randomized Trial

NCT 02487225

January 9, 2017

TITLE AND SUMMARY PAGE

Project Title: Pentoxifylline Treatment in Acute Pancreatitis; A Double-Blind Placebo-Controlled Randomized Trial

Principal Investigator:

[name] [name]
Section of Gastroenterology and Hepatology
Professor of Medicine
Mayo Clinic College of Medicine
[name]
[contact]
[contact]
[contact]

Participating Investigators:

[name].
[name].
[name]

Project Summary:

Background. Acute pancreatitis (AP) is a cause of significant morbidity and mortality and effective therapeutic regimens to treat this condition are lacking. Extensive experimental evidence indicates that tumor necrosis factor alpha (TNF- α) contributes to the pathogenesis of multiple organ failure (main cause of morbidity and mortality) in AP, suggesting a possible role for inhibition of TNF- α in the treatment of AP. There is no effective drug therapy for AP and hardly any human experience about the role of pentoxifylline in AP Methods: Randomized, double-blind, placebo-controlled study comparing three times daily dosing with Pentoxifylline from the time of admission until 72 hours of hospitalization in patients presenting with AP. Seventy-five patients will be enrolled in both the "treatment" and "placebo" groups (150 patients total). This study will be performed at Mayo Clinic, Rochester. Primary outcomes: Determine changes in CRP, TNF- α , IL-6, and IL-8 levels from admission baseline at one week.

Significance: If our hypothesis is confirmed this trial will be a landmark development in the treatment of AP. A simple, safe, and inexpensive drug that can be given to all patients with AP, in all settings, will be available to decrease the significant morbidity and mortality due to this disease.

PROJECT DESCRIPTION

Specific Aims:

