Aim1: Determine if oral pentoxifylline will improve clinical outcomes in AP. Persistent SIRS and organ failure, pancreatic and/or peripancreatic necrosis and infection (determinants) will be primary endpoints, while death (infrequent), length of stay, and the need for ICU and intervention will be secondary endpoints. These are all identified in the revised Atlanta classification as outcomes of interest. Hypothesis: Pentoxifylline will decrease the occurrence of any one of the following adverse outcomes in AP: pancreatic and/or peripancreatic necrosis and infection, persistent organ failure, prolonged hospital stay, need for ICU, and intervention and death in patients with AP.

Aim2: Determine if oral pentoxifylline will decrease serum levels of inflammatory markers.
Hypothesis: Pentoxifylline will reduce levels of CRP, TNF- α , IL-6, and IL-8, and this reduction will correlate with clinical outcomes in patients with AP.

Background and Significance:

Acute pancreatitis, an inflammation of the pancreas gland, is the most common gastrointestinal hospital discharge diagnosis and averages \$2.6 billion in costs per year. Yet, as common as it is, there is no specific drug to treat this disease. There has been no drug trial in AP since the beginning of this century. Based on previous animal studies and a pilot study in humans at our institution, pentoxifylline has shown to block the inflammation in this disease. A larger study must be performed before the efficacy of this drug can be confirmed. A successful study would provide a breakthrough in AP therapy, paving the way for a simple, safe, and inexpensive drug to be available world-wide to treat this disease. This novel approach would be a major advancement in the treatment of this disease.

Acute pancreatitis (AP) is a common inflammatory condition of the pancreas leading to the hospitalization of millions of patients annually worldwide. While the majority of patients (~80%) have mild, self-limiting disease with low mortality, severe acute pancreatitis (SAP) is associated with high morbidity and mortality (20-40%) and prolonged hospital stays. Specific pharmacological therapies, such as aprotinin, glucagon, gabexate, somatostatin and lexipafant, have not been shown to have any advantage in randomized controlled trials. As a result, treatment for AP is mainly supportive involving bowel rest, aggressive intravenous fluid resuscitation and pain control -a targeted therapy for AP is therefore urgently needed.

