2. Pentoxifylline reduces the blood levels of inflammatory markers, which correlates with improvement in clinical outcomes. This study is a novel, exploratory clinical study of the effect of a drug that has a proven role in animal studies in blocking the inflammatory response in AP. It is also a high reward study that will lead to a breakthrough in the treatment of AP and challenge the age old recommendation of supportive treatment alone.

The study will have 2 groups of 75 patients each, all with AP, randomly assigned to either the drug or a placebo, which looks like the drug, for a period of 3 days or until the time they are discharged, if hospital discharge is within 7 days of admission. The levels of markers of inflammation (CRP, IL-6, IL-8 and TNF- α) will be measured at baseline and on 5 successive days or until the time of discharge, whichever occurs earlier. Determination of group size was based on the previous pilot study to decrease any of the important adverse outcomes, providing for a dropout rate of 10% during the study. During 2012, 263 patients with AP were admitted to this institution, which possesses the needed infrastructure for successful completion of clinical drug intervention trials. In the stipulated period of 2 years by the NIH, the required number of patients for the study could be recruited.

This project represents a single center study at Mayo Clinic Rochester. The trial is a randomized, double-blind, placebo-controlled study design.

Subjects: Subjects will be adult patients 18 years of age and greater which will be recruited from Mayo Clinic and admitted to the hospital with acute pancreatitis as defined by at least two of the following:

- amylase and/or lipase greater than 3 times the upper limit of normal values,
- characteristic cross-sectional imaging,
- characteristic pain syndrome.

If patients give consent to be in the study the PI may contact those patients before formally enrolling them in the study. By overseeing that one of the team (a study coordinator, PI, and co-investigator) is present during the weekends, we anticipate that those eligible patients during the weekend period are not going to be excluded.

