Randomization will be performed by the pharmacy under the direction of the study statistician, using randomized blocks, to ensure all clinical study personnel are blinded to patient allocation throughout the study. Subjects will be randomized into two groups. The "treatment group" will receive Pentoxifylline 400 mg one to three times daily by mouth from the time of enrollment until 72 hours from enrollment. Subjects will receive up to maximum of 9 doses of this medication. The "control" group will receive placebo dosing at similar intervals. Randomization will occur in a block fashion. Study medication will be administered at 1x/day if creatinine clearance \leq or \geq 30ml/min. per the manufacture prescribing information. All other treatment for AP (fluid resuscitation, antibiotics, surgical intervention, pain control, etc.) will be at the discretion of the primary care team. However, the study investigators will ask primary teams to follow standardized treatment guidelines for acute pancreatitis (to control for intravenous hydration and enteral nutrition, which may influence IL levels).

Blinding: Both subjects and investigators will be blinded to the randomization.

Sample Size:

We propose testing 75 patients in each study arm. Our primary outcome will be whether the patient develops any of the following outcomes of moderate or severe AP: hospital stay longer than 10 days, admittance to the ICU, persistent organ failure, pancreatic and/or peripancreatic necrosis and infection, SIRS, need for intervention, or death. In our pilot study, 7.1% of the patients on pentoxifylline experienced at least one of these outcomes, compared to 28.6% of those on the placebo. If extrapolated to the larger RCT, this reduction in events of these critical outcomes (7.1% vs. 28.6%) would represent a significant and meaningful difference for patients. Using a 5% 2-sided type I error, 58 patients in each group would be needed to achieve 80% power to detect the anticipated difference. In order to account for the unlikely event of up to 10% study dropout, we plan to enroll 64 patients in each group. We will use a randomized block design stratifying for predicted disease severity (mild, moderate, or severe).

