Data Collection and Handling: TNF- α , Il-6, and Il-8 will be handled by the research blood draw division of Mayo Clinic per usual practice. The C-RP testing on days 1, 3, 4 and 5 will be handled by the research blood draw division of Mayo Clinic per usual practice. The clinical and research laboratory data will be recorded every day until discharge. Early discharges before completion of 3 days of drug or 5 days of study of markers after drug administration is not considered as protocol violation and data until the time of discharge will be recorded for the purpose of analysis. Data Safety Monitoring Board (DSMB) will be constituted by clinicians having experience in TNF- α blockade therapy.

Data Analysis: All access to data will be password protected. Analysis will be on an-intent-to-treat basis. Outcomes will primarily be descriptive statistics such as means and percents. Continuous secondary end points will be analyzed with the t-test if the data are normally distributed and the Wilcoxon Rank Sum test if non-normal. Analyses of dichotomous secondary end points will use either the Chi-squared test or Fisher's Exact Test comparing proportions. Kaplan-Meier will be used to estimate survival. An interim analysis of data for preliminary review of less than target accrual may be done.

Feasibility: Nearly 250 patients with acute pancreatitis are seen at Mayo Clinic hospitals every year. Assuming ~60% of them are directly admitted to Mayo Clinic (not transferred from outside), and 50% agree to participate in the study it would take 24 months at Mayo to recruit 150 patients. If recruitment goals are not reached at Mayo Clinic after ~24months, the study may have to be extended for 6 months more. **Deliverables:**

We expect to publish at least one manuscript in a major academic journal as a result of this work. Our hope is that any reduction of morbidity or mortality from the novel therapy will have a profound effect on the treatment of acute pancreatitis and lead to future expanded clinical trials.

TAILED MILESTONES SCHEDULE

Endpoints:

May 2015 Mayo Institutional Review Boards (IRB) approval.

June 2015 Approximate NIH will release funds when IRB approved protocol is provided.

July 2015 - Approximate Patient enrollment begins at Mayo

April 2016 Approximate Data Safety Monitoring Board (DSMB) contact via teleconference or E-mail meeting to meet biannually and/or not less-than once a year.

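### Three different primary outcomes are stated; only the composite is powered, the one-week biomarker outcome has no scheduled sample, and no primary has an assigned test

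*Combined protocol and SAP*

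**What the plan says.** Three sections of the combined protocol and SAP name a primary outcome.

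- **Project Summary:** the change in CRP, TNF-α, IL-6 and IL-8 "levels from admission baseline at one week".
- **Specific Aims, Aim 1:** "Persistent SIRS and organ failure, pancreatic and/or peripancreatic necrosis and infection (determinants) will be primary endpoints". The same sentence gives four other clinical outcomes a lower rank: "while death (infrequent), length of stay, and the need for ICU and intervention will be secondary endpoints".
- **Sample Size:** "Our primary outcome will be whether the patient develops any of the following outcomes of moderate or severe AP". The list is a hospital stay over 10 days, ICU admission, persistent organ failure, "pancreatic and/or peripancreatic necrosis and infection, SIRS, need for intervention, or death".

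Experimental Design ties the sample size to the clinical composite: "Determination of group size was based on the previous pilot study to decrease any of the important adverse outcomes".

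On sampling, the same section says the markers "will be measured at baseline and on 5 successive days or until the time of discharge, whichever occurs earlier". The table under Laboratory test and assessments has columns for Day 0 to Day 5 only. Data Collection and Handling adds that leaving before "5 days of study of markers after drug administration is not considered as protocol violation", and that data are recorded until discharge.

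The Data Analysis section describes outcomes as mainly descriptive. It assigns the t-test or Wilcoxon test to continuous secondary end points and chi-squared or Fisher's exact test to dichotomous secondary end points. Kaplan-Meier is listed for estimating survival. No test is given for a primary outcome.

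**The concern.** The three statements cannot all hold. Death, length of stay, ICU need and intervention can decide the primary result under Sample Size but are secondary under Aim 1. SIRS must be persistent under Aim 1 but carries no qualifier in the composite. The biomarker statement concerns a different kind of outcome, at a time point that the sampling schedule does not reach.

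The same data could therefore give different primary answers. If the composite is null but one biomarker or one determinant differs between arms, the text supports calling that result primary. If the composite is positive because of ICU admissions and long stays, Aim 1 supports calling it secondary. With no primary test named, the choice between chi-squared and Fisher is also open until the data are seen.

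**Working it through.** **1. Which outcome sets the sample size?** Inputs from Sample Size: p₁ = 0.071, p₂ = 0.286, two-sided α = 0.05, power 80%. So p̄ = 0.1785 and |p₁ − p₂| = 0.215.

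Pooled formula: n = [1.960·√(2p̄(1−p̄)) + 0.8416·√(p₁(1−p₁)+p₂(1−p₂))]² / 0.215² = [1.960·0.5415 + 0.8416·0.5198]² / 0.046225 = 48.6, so 49 per group.

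Continuity correction: n′ = (n/4)·[1 + √(1 + 4/(n·0.215))]² = 57.5, so **58 per group**, as the plan states. Then 58 × 1.10 = 63.8, which gives the stated 64.

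The composite therefore drives the size. The plan gives no standard deviation or target difference for any biomarker and no design rate for a single determinant, so neither alternative primary has a power statement and none can be derived.

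**2. The rival definitions compared**

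| Item | Project Summary | Aim 1 | Sample Size |
|---|---|---|---|
| Four biomarkers | primary | – | – |
| SIRS | – | primary (persistent) | in primary (unqualified) |
| Persistent organ failure | – | primary | in primary |
| Necrosis and infection | – | primary | in primary |
| Death, stay, ICU, intervention | – | secondary | in primary |

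**3. Why the SIRS wording matters.** The pilot had 14 patients per arm (Preliminary Results), so 7.1% is 1/14 and 28.6% is 4/14. That section reports no pentoxifylline patient with a stay over 10 days, ICU need, persistent organ failure, intervention or death. The single pentoxifylline event must then have been necrosis/infection or SIRS. The SIRS definition therefore bears directly on the rates behind the sample size.

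**4. Can the one-week outcome be observed?** Counted from the Day 0 baseline, the last scheduled draw is Day 5, or earlier with discharge. The later follow-up, by telephone or record review at about 4 months, lists no marker draw. No one-week sample is scheduled.

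**5. Does the choice of test matter?** Power for the composite by full binomial enumeration at the design rates:

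| Evaluable per arm | Fisher | Chi-squared, uncorrected |
|---|---|---|
| 58 | 0.827 | 0.889 |
| 64 | 0.871 | 0.911 |
| 75 | 0.922 | 0.952 |

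A borderline example at 75 per arm: 6 versus 15 events gives p = 0.034 by uncorrected chi-squared and p = 0.058 by Fisher.

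**6. Multiplicity, for illustration only.** The plan states 5% for the composite alone. If the four biomarkers were each tested at 5%, the chance of at least one false positive would be 1 − 0.95⁴ = 18.5% if independent. By simulation of equicorrelated normals it would be about 15.5% at an assumed correlation of 0.5 and about 11.4% at 0.8.

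**The case against.** The strongest reply is that the composite is plainly intended. The Aim 1 hypothesis speaks of reducing any one of a list of adverse outcomes that nearly matches the composite, clinical aims come before biomarker aims throughout, and group size was set on the composite. This supports choosing the composite as the primary. It does not remove the conflict: that hypothesis omits SIRS, it follows a sentence calling four of its items secondary, and nothing in the text overrides the Project Summary.

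Second, choosing between chi-squared and Fisher afterwards does little harm to type I error. Taking the smaller p-value at 58, 64 or 75 per arm, with common event rates from 7.1% to 31%, gives about 4.8% to 5.3%. At the design rates with 75 per arm, the two tests disagree in about 3% of trials. This stands. The open test matters for a borderline table and is the lesser part of the problem.

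Third, the plan calls its outcomes mainly descriptive, and nowhere says that each biomarker is tested at 5%. That is why the multiplicity figures are only an illustration. But the plan also sets a two-sided 5% error and 80% power and says that the study would validate efficacy, which is confirmatory use.

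Fourth, Day 0 is not defined against admission, and enrollment may come up to 72 hours after diagnosis. Day 5 could fall about a week after admission for some late enrollees. That would be incidental, and it would not give a common one-week value.

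Finally, naming one primary still leaves the composite without a time window, and Day 5 marker values will be missing for patients discharged early. Both points are fair, and the fix should cover them.

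**Conclusion.** The concern holds and must be fixed. Three sections name different primary outcomes, with no rule to rank or combine them. Only the composite is powered, and its 58 per group reproduces. The one-week biomarker outcome has no scheduled sample, and no stated primary has an assigned test.

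The main consequence is freedom to choose which result is called primary. That cannot be reduced to one error rate without knowing how the endpoints correlate and which would be tested. The power figures assume that the 14-per-arm pilot rates hold and that the stated numbers are all evaluable. With 10% dropout from 75 (67.5, so about 67 evaluable), Fisher power is about 0.89. From 64 (57.6, so 57 to 58) it is about 0.82 to 0.83.

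**What to change.** 1. Name the seven-item composite as the single primary endpoint in the Project Summary, Aim 1 and Sample Size.
2. In Data Analysis, assign it one test at two-sided 5%. Fisher's exact test is already listed and is a defensible choice; the essential step is to fix the test in advance.
3. Label the individual clinical components and the four biomarkers as secondary throughout.
4. Replace the one-week marker time point with a named day on the Day 0–5 schedule (Day 5 is nearest), and say how values missing after discharge are handled.
5. Reconcile SIRS with persistent SIRS, using the definition that produced the pilot rates of 7.1% and 28.6%.
6. State the period over which composite events count.

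The cost is wording in four sections and a check of the pilot records. No new visits or samples are needed. The sponsor gives up a biomarker or single-determinant primary claim, and accepts slightly lower power with Fisher than with uncorrected chi-squared (0.92 against 0.95 at 75 per arm). The document is dated January 2017 and enrollment was planned from about July 2015, so the change should be a dated amendment made without knowledge of outcomes by arm.

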
Preliminary Results:

We have already successfully conducted a pilot double-blinded, placebo-controlled, allocation-blinded RCT of oral pentoxifylline in patients with AP with any one of several reported predictors of severe disease. By selecting many reported predictors of severity, we attempted to avoid as many patients with a mild form of the disease as possible. Both groups had 14 patients, evenly matched for age and sex; APACHE II and SIRS scores at admission; and pancreatic and/or peri-pancreatic necrosis. Compared to the placebo group, the pentoxifylline group experienced a 29% reduction in length of hospital stay, a 29% reduction in the need for an ICU stay, a 21% reduction in persistent organ failure, and a 7% reduction in pancreatic necrosis or fluid collection. The reductions translated to having no patients with: hospital stays over 10 days, an ICU need, persistent organ failure, interventions, or death in the pentoxifylline group . However, with the small sample size of this pilot study, these clinically significant differences failed to achieve statistical significance except for ICU need. There was no difference in the

inflammatory markers between the two groups over a short period of three days. We concluded that it is feasible to conduct a drug intervention study in a single institution, and pentoxifylline appeared safe and decreased the length of stay and the need for ICU intervention. With larger numbers, besides validating the above findings, we expect to see a beneficial

Experimental Design or Project Summary:

Acute pancreatitis (AP) is an inflammation of the pancreas gland and the most common gastrointestinal discharge diagnosis (approximately 280,000 admissions in 2009). It has resulted in \$2.6 billion, annually, in health care costs, mainly due to the more serious forms of the disease. Lack of any specific drug to treat the condition and predictors to identify patients who will develop more serious forms of the disease contribute to this. Long-term objectives of the study are to find a drug to treat this disease, improve patient outcomes, and reduce the costs of health care. Based on our experience with animals and a small, human subjects pilot study, our hypothesis and specific aims are:

1. Pentoxifylline, administered within 72 hours of diagnosis, improves the clinical outcomes and decreases the occurrence of more serious forms of AP.

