Patients admitted within 24 hours with AP diagnosis will be included, with the exception of those meeting the exclusion criteria. Those patients that have been identified with AP diagnosis within 72 hours will be approached by the study coordinator and also by the principal investigator (PI) (whenever feasible) to explain the study and obtain written consent.

Inclusion criteria

- Enrollment within 72 hours of diagnosis of AP
- Ability to give informed consent or a legal adult representative LAR able to give informed consent for subject when needed as defined but LAR use guidelines.
- Adult subjects of age ≥ 18 years.

Exclusion Criteria:

- Moderate or severe congestive heart failure,
- History of seizure disorders or demyelinating disease,
- Nursing mothers,
- Pregnancy,
- History of prior tuberculosis or risk factors for tuberculosis
- Evidence of non- corticosteroid immunosuppression (such as malignancy, chronic renal failure, chemotherapy within 60 days, and HIV)
- Evidence of active hemorrhage,
- Paralytic ileus with severe nausea and vomiting.

Laboratory test and assessments:

Test / Procedure	Day 0	Day 1	Day 2	Day 3	Day 4	Day 5
TNF-a*	X	X	X	X	X	X
IL-6*	X	X	X	X	X	X
IL-8*	X	X	X	X	X	X
Pregnancy Test X						
CRP	X*	X*	X*	X*	X*	X*

* Note: The C-RP, TNF-a, IL-6, IL-8 tests are charged to the research study. All other tests listed are clinical standard care for acute pancreatitis.

The pregnancy test may be done as standard of care and will be closely monitored by study staff to assure completion before subject receives study medication.

Follow up process may be done by telephone contact or review of medical records dependant on subjects follow-up information availability. Some subjects may do their follow up visits at a

local facility not return to Mayo Clinic Rochester for follow up visit within the 4 month time frame (plus or minus 15 days). Thus their medical record may not be available in the Mayo Network system. Then a telephone contact may be done to acquire the follow up information.

Randomization:

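### The powered composite counts unqualified SIRS and has no working rule for components already present at enrolment, so the stated 80% power is unsupported until the counting rule is fixed and matched to the pilot rates

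*Combined protocol and SAP*

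**What the plan says.** The trial is sized on a composite in the Sample Size section. A patient has an event on developing any one of several outcomes of moderate or severe disease. The list opens with a long stay, ICU admission and persistent organ failure, and ends with "pancreatic and/or peripancreatic necrosis and infection, SIRS, need for intervention, or death". Organ failure is qualified as persistent; SIRS, in the same sentence, is not.

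Aim 1 under Specific Aims is narrower on SIRS: "Persistent SIRS and organ failure, pancreatic and/or peripancreatic necrosis and infection (determinants) will be primary endpoints".

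The entry window, under Inclusion criteria, is "Enrollment within 72 hours of diagnosis of AP". No eligibility criterion excludes a patient who already has SIRS, necrosis or an ICU stay, and study drug starts at enrolment.

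Preliminary Results lists among the features on which the pilot arms were matched "APACHE II and SIRS scores at admission; and pancreatic and/or peri-pancreatic necrosis".

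The size calculation takes its rates from that pilot: "7.1% of the patients on pentoxifylline experienced at least one of these outcomes, compared to 28.6% of those on the placebo". It concludes: "Using a 5% 2-sided type I error, 58 patients in each group would be needed" "to achieve 80% power to detect the anticipated difference". The section then gives 64 per arm after dropout, while also proposing 75 per arm.

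**The concern.** The two statements of the primary endpoint give different counts. Under Aim 1, transient SIRS is not an event. Under the Sample Size wording it can be, and a patient may arrive with it up to three days after diagnosis. ICU admission and necrosis raise the same question of timing.

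A component present before the first dose cannot be prevented by the drug. Randomisation spreads such patients evenly between arms, and stratifying on predicted severity makes the balance closer, but neither removes their events. If they are counted, both event rates rise, the difference shrinks, and a drug that works could look ineffective. The plan does not say whether they are counted. Two adjudicators could classify a patient with SIRS on Day 0 differently, and both could cite the same sentence. A rule chosen after the data have been seen would not be credible.

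**Working it through.** **Inputs**

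- Event rates 28.6% (placebo) and 7.1% (pentoxifylline), two-sided 5%, 80% power, 58 per arm: Sample Size.
- Pilot arms: "Both groups had 14 patients, evenly matched for age and sex" (Preliminary Results), so the rates are 4/14 and 1/14.
- Planned size 75 per arm, 10% dropout: Sample Size. 75 × 0.9 = 67.5, taken as 67 evaluable.
- f, the share of patients who already meet a component at enrolment: not in the documents. Assumed range 0 to 30%.

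**Step 1: reproduce the plan's figure.** With p₁ = 0.286, p₂ = 0.071, d = 0.215 and mean p̄ = 0.1785:

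n = [1.960·√(2p̄(1−p̄)) + 0.842·√(p₁(1−p₁) + p₂(1−p₂))]² / d²

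= [1.960·√0.2933 + 0.842·√0.2702]² / 0.0462 ≈ 48.6, that is 49.

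With continuity correction: n/4 · [1 + √(1 + 4/(n·d))]² = 12.15 × (1 + √1.383)² ≈ 57.5, that is **58 per arm**. The plan's figure is matched.

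**Step 2: dilution model (assumption).** A share f in each arm counts as an event whatever the treatment, and the pilot rates apply to the rest:

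rate = f + (1 − f)·p, so the difference becomes (1 − f) × 0.215.

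Example, f = 10%: placebo 0.10 + 0.90 × 0.286 = 35.7%; pentoxifylline 0.10 + 0.90 × 0.071 = 16.4%; difference 19.3 points.

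**Step 3: power.** Two-sided Fisher exact test at 5%, by enumerating every pair of event counts and summing the binomial probabilities of the pairs that reject:

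| f | Placebo vs drug | 58 per arm | 67 per arm | 75 per arm |
|---|---|---|---|---|
| 0 | 28.6% vs 7.1% | 83% | 89% | 92% |
| 5% | 32.2% vs 11.7% | 71% | 78% | 83% |
| 10% | 35.7% vs 16.4% | 60% | 67% | 73% |
| 20% | 42.9% vs 25.7% | 42% | 49% | 54% |
| 30% | 50.0% vs 35.0% | 30% | 35% | 42% |

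The continuity-corrected approximation agrees within about 3 points. The uncorrected chi-square is more favourable, but at 75 per arm it also falls below 80% at f = 10% (78%). With the continuity-corrected formula used for the plan's 58, 80% power needs 73 per arm at f = 5%, 90 at 10%, 130 at 20% and 182 at 30%.

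**Step 4: what did the pilot count?** Preliminary Results reports that no pentoxifylline patient had a stay over 10 days, ICU need, persistent organ failure, an intervention or death. The only components left for that arm are SIRS and necrosis/infection, and 7.1% is 1 of 14. So at most 1 of 14 patients, all selected for predictors of severe disease, was counted for either. That is few if any SIRS at any time was an event. It suggests, without proving, that the pilot used a narrower count than the Sample Size sentence describes.

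**The case against.** The strongest reply has four parts.

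*'Develops' means new onset.* On the ordinary reading, a patient who has SIRS or is in the ICU on Day 0 does not go on to develop it. This stands in part. A reader might infer that the plan contains a rule that counts pre-existing events; it does not. But the word comes with no onset time, baseline reference or duration, and it does not resolve SIRS against persistent SIRS.

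*The pilot rates are stated to be for the same outcomes.* If the pilot counted events present at entry, the dilution is already inside 7.1% vs 28.6%, and 58 per arm still gives 80%. This stands as one branch, and the table above does not apply to it. Under that branch the pre-existing share in the pilot's pentoxifylline arm was at most 1/14 = 7.1%. The documents do not say which branch is true.

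*75 per arm leaves slack over 58.* True for small f: power is 83% at f = 5% with no dropout. With the plan's own 10% dropout it is 78%, so the slack is thin.

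*The evidence on baseline status is limited, and the data will exist.* Matching on SIRS scores at admission does not say how many patients met SIRS. The timing of the necrosis item is unclear, and the same section also reports necrosis or fluid collection as an outcome. Data Collection and Handling has clinical data recorded daily until discharge, and stratifying on predicted severity needs a baseline assessment. All of this stands. A reader should not conclude that baseline status cannot be recovered. What is missing is a rule for using it.

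**Conclusion.** The concern holds in a conditional form. Aim 1 and the Sample Size section conflict on SIRS, and no operational rule separates components present at entry from new ones. The 80% power is therefore unsupported unless only new-onset components and persistent SIRS count, or the pilot rates are shown to follow the same counting rule as the trial.

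If the pilot rates are new-event rates and the trial also counts components present at entry, a 10% share brings power to 60% at 58 per arm, 67% at 67 and 73% at 75. This rests on the assumed f and on the pilot rates applying unchanged to the remaining patients.

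A reader might go further and conclude that the stated power has been lost. The documents do not support that: f is not given, 'develops' can be read as new onset, and the pilot rates may already contain such events. Confidence is moderate.

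**What to change.** 1. In the Sample Size section, replace SIRS with persistent SIRS, as in Aim 1, and state the duration.
2. Record the status of each component at Day 0 from chart data. Count a component only if it was not documented at Day 0 and was first met after randomisation. Counting from randomisation rather than first dose fits the planned intention-to-treat analysis.
3. SIRS present at Day 0 counts only if it meets the persistence definition after randomisation.
4. No baseline imaging is scheduled, so absence of necrosis at entry cannot be confirmed for every patient. State in advance how necrosis is classified when there is no baseline image.
5. Keep every patient in the intention-to-treat set. A patient with one component at Day 0 stays at risk for the others.
6. State which counting rule produced 7.1% and 28.6%. If it differs from the rule adopted, restate the power from rates counted the same way.

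The cost is a wording change, a short Day 0 checklist and a look back at the pilot's event counts. The event rate may be somewhat lower, so item 6 is needed: changing the definition alone does not establish 80% power.
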